
f. Only guselkumab clinical responders at Week I 12 and placebo crossover responders at Week I 24 will be rerandomized in the Maintenance Study. Guselkumab 24 Week responders and induction placebo responders at Week I 12 will enter the Maintenance study but will not be rerandomized.
 
g. All assessments are to be completed before study intervention administration, unless otherwise specified. It is recommended that PRO assessments be completed first.
 
h. For all assessments not marked at this visit, data from the study assessments performed at the Week I 12 visit (for participants in clinical response at Week I 12) or at the Week I 24 visit (for participants who were not in clinical response at Week I 12 but were in clinical response at Week I 24) will be used for the Week M 0 visit.
 
i. A participant who meets the criteria for clinical flare for the first time prior to Week M 32 should undergo an endoscopy (which need only be a flexible sigmoidoscopy) to determine loss of clinical response based on the modified Mayo score (Section 4.1.3.1).
 
j. If TB is suspected at any time during the study, a chest radiograph and QuantiFERON TB[®] (or T SPOT[®] for sites in Japan) test should be performed. In countries/territories where the QuantiFERON TB[®] test is not registered/approved, TB skin testing should also be performed (recommended but not required for study centers in Ukraine if tuberculin is not available).
 
k. Temperature, pulse/heart rate, respiratory rate, and blood pressure. At a study intervention administration visit, vital signs should be obtained before and approximately 30 minutes after SC injection, or if the participant reports any symptoms.
 
l. A urine pregnancy test must be performed before any study intervention administration for women of childbearing potential.
 
m. The C SSRS should be completed after all PROs and before any other tests, procedures, or other consultations to prevent influencing participant perceptions.
 
n. An injection site reaction is any adverse reaction at any SC study intervention injection site. Injection sites will be evaluated for reactions and any injection site reaction should be recorded as an adverse event.
 
o. Predose samples should be collected at all dosing visits before study intervention administration. All reasonable attempts should be made to collect samples at the scheduled time points and record the actual dates and times of sample collections.
 
p. Colonic biopsy samples will be collected from all participants during endoscopy for histologic assessment and RNA transcriptomic analysis. Pre defined sites will collect adjacent biopsy samples to support exploratory single cell isolation and analyses.
 
q. Whole blood samples will be collected for PBMC isolation from a subset of participants that provide biopsy samples for single cell analyses at selected sites. Whole blood (PBMC) samples should be collected within ±3 days of the endoscopy visit.
 
r. Serum biomarkers will be measured in all participants to evaluate the effects of study intervention on inflammatory proteins associated with UC, including cytokines associated with the IL 23 pathway.
 
s. Whole blood (RNA) will be measured in all participants to evaluate the molecular effects of study intervention in UC.
 
t. Fecal biomarkers may be used for evaluation of changes in inflammatory proteins or microbiome composition.
 
u. Participants who complete the safety and efficacy evaluations (including the required endoscopy procedure) at maintenance Week M 44 and who may benefit from continued study intervention, in the opinion of the investigator, will have the opportunity to participate in the LTE of the Maintenance Study.
 
v. At visits also requiring endoscopy, stool samples should be collected prior to the initiation of endoscopy bowel preparations. Refer to the At Home Stool Collection Manual for detailed instructions.
 
w. Should be completed if the Week M 0 visit is completed on a day other than that of the Week I 12 visit or Week I 24 visit.
 
x. Corticosteroid tapering must begin at M 0 for all participants receiving corticosteroids at baseline. Refer to Section 6.5.1 for guidance and requirements for corticosteroid use.
														

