The power for detecting a treatment difference between the guselkumab 200 mg SC q4w and the placebo group for the primary endpoint and each of the major secondary endpoints with 484 participants in the primary analysis population is shown (Table 9). The assumptions about the proportion of participants achieving the primary endpoint and each major secondary endpoint have been based on data from the CNTO1275UCO3001 maintenance study.

Table 9: Power for Detecting a Treatment Effect for the Primary Endpoint and Each of the Major Secondary Endpoints With 484 Participants in the Primary Analysis Population (161 in Each Treatment Group)			
	Proportion of participants achieving the endpoint		Power^a (%)
	Placebo	Guselkumab	
Primary endpoint			
Clinical remission at Week M-44	25	45	97
Major secondary endpoints			
Symptomatic remission at Week M-44	45	68	99
Endoscopic healing at Week M-44	30	50	96
Clinical response at Week M-44	51	77	99
Histologic-endoscopic mucosal healing at Week M-44	26	46	97
IBDQ remission at Week M-44	40	60	95
Fatigue response at Week M-44	26	55	>99
Corticosteroid-free (ie, not requiring any treatment with corticosteroids for at least 8 weeks prior) clinical remission at Week M-44	25	42	90
Clinical remission at Week M-44 among the participants who had achieved clinical remission at maintenance baseline^b	36	61	74
Endoscopic normalization at Week M-44.	18	29	65

a: Based on testing the SC guselkumab 200 mg q4w group versus placebo at $\alpha=0.05$ (2-sided).

b: It is estimated that about 33% of participants in the primary analysis population (53 participants per treatment group) will be in clinical remission at Week M-0.

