3. SAMPLE SIZE DETERMINATION

Key efficacy analyses in the Maintenance Study will be based on the **Randomized Full Analysis Set** (primary population), which includes all participants with a modified Mayo score of 5 to 9 who are randomized (i.e., Guselkumab clinical responders at Week I-12 and Placebo crossover responders at Week I-24 in an Induction Study) in the Maintenance Study who received at least 1 dose of study intervention in this Maintenance Study (Section 4). It is expected that very few participants in the randomized population would not receive study intervention. Therefore, for the purpose of sample size consideration, we will assume the **Randomized Full Analysis Set** is the same as the randomized population with a modified Mayo score of 5 to 9. Unless otherwise stated, the sample size/power calculations in this section refer to the primary population.

A multiplicity-controlled testing procedure, starting with the high guselkumab dose group (200 mg SC q4w), will be used to control the overall Type-I error rate at the 0.05 level (2-sided) over the primary and major secondary endpoints. As such, sample size/power calculations were based on the chi-square test to detect a significant difference between participants receiving SC guselkumab 200 mg q4w and those receiving placebo.

The assumptions for the sample size calculations were based on data from the Phase 3 ustekinumab (anti IL 12/23 mAb) CNTO1275UCO3001 study, which was conducted by the sponsor in a very similar target population, i.e., participants with moderately to severely active UC who had failed or were intolerant to biologic or conventional therapies. In CNTO1275UCO3001, the proportions of participants in clinical remission at Week 44 were 26.3% and 44.9% for placebo and ustekinumab 90 mg SC q8w, respectively, for a treatment difference of 18.6%. Based on these data, the clinical remission at Week M-44 rates are assumed to be 25% for placebo and 45% for each of the guselkumab doses. Given these assumptions, 118 participants in each group (354 participants in total) will provide statistical power of 90% at a significance level of 0.05 (2 sided) for the primary endpoint. However, the actual power can vary depending on the proportions of participants in clinical remission. Examples are presented below in Table 1:

Table 1:Power for Detecting a Treatment Effect Based on Different Proportions of Participants in Clinical

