Group A=Participants in clinical response to IV guselkumab induction at Week I-12; Group B=Participants not in				

clinical response to IV guselkumab induction at Week I-12; Group B=Participants not in clinical response to IV placebo induction at Week I-12 but in clinical response at Week I-24 after receiving induction IV guselkumab at Weeks I-12, I-16, and I-20.

a: The proportion of participants not in clinical response to IV placebo induction at Week I-12 and did not discontinue study intervention is assumed to be 60%.

With 484 participants in the primary population, the power for detecting a treatment difference between the guselkumab 200 mg SC q4w group and the placebo group for the primary endpoint and for each of the major secondary endpoints is shown below in Table 3. The assumptions about the proportion of participants achieving the primary endpoint and each major secondary endpoint have been based on data from the CNTO1275UCO3001 maintenance study.

Table 3:Power for Detecting a Treatment Effect for the Primary Endpoint and Each of the Major
Secondary Endpoints With 484 Participants in the primary population (about 161 in Each
Treatment Group)

	Proportion of participants achieving the endpoint		
	Placebo	Guselkumab	Power ^a (%)
Primary endpoint			
Clinical remission at Week M-44	25	45	97
Major secondary endpoints			
Symptomatic remission at Week M-44	45	68	99
Endoscopic healing at Week M-44	30	50	96
Clinical response at Week M-44	51	77	99
Histologic-endoscopic mucosal healing at Week M-44	26	46	97
Corticosteroid-free (i.e., not requiring any treatment with corticosteroids for at least 8 weeks prior) clinical remission at Week M-44	25	42	90
IBDQ remission at Week M-44	40	60	95
Fatigue response (≥ 7-point improvement) at Week M-44	26	55	>99
Clinical remission at Week M-44 among the participants who had achieved clinical remission at maintenance baseline ^b	36	61	74
Endoscopic normalization at Week M-44.	18	29	65

will be in clinical remission at Week M-0.

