5.4.1.3. Main Estimators (Analyses) for the Secondary Estimands

The major secondary endpoint analyses will be based on the **Randomized Full Analysis Set**. For all statistical comparisons of the major secondary endpoints (except for clinical remission at Week M-44 among the participants who had achieved clinical remission at maintenance baseline), a CMH test (2-sided) stratified by clinical remission status at maintenance baseline (Yes/No) and induction dose treatment (guselkumab 400 mg, guselkumab 200 mg, placebo crossover to guselkumab 200 mg) will be used. In cases of rare events, Fisher's exact test will be used for treatment comparisons.

For clinical remission at Week M-44 among the participants who had achieved clinical remission at maintenance baseline, a CMH test (2-sided) stratified by induction dose treatment (guselkumab 400 mg, guselkumab 200 mg, placebo crossover to guselkumab 200 mg) will be used.

Summaries of the proportion of participants achieving each major secondary endpoint by treatment group as well as the associated 95% confidence interval, the adjusted treatment difference (with Cochran-Mantel-Haenszel weight) between each guselkumab treatment group and the placebo group, as well as the associated 95% confidence interval will be presented.

Missing Data Rules for the Secondary Estimands:

After accounting for the ICE strategies, any missing data for the major secondary endpoints will be handled with nonresponder imputation. In particular, the following rules will be used:

[figure not shown]
- Participants who are missing any or all of the 3 Mayo subscores that comprise the modified Mayo score will be considered not to have achieved corticosteroid-free clinical remission, maintenance of clinical response, or maintenance of clinical remission.
- Participants who have a missing endoscopy subscore at Week M-44 will be considered not to have achieved endoscopic healing or histologic-endoscopic mucosal healing or endoscopic normalization at Week M-44.
- Participants who are missing any or all of the components in the Geboes grading system pertaining to histologic healing endpoint will be considered not to have achieved histologic-endoscopic mucosal healing.
- Participants who are missing either stool frequency or rectal bleeding subscores at Week M-44 will be considered not to have achieved symptomatic remission at Week M-44.

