6.3. Appendix 3 Demographics and Baseline Characteristics

Table 6 presents a list of the demographic variables that will be summarized by treatment group, combined active treatment group, and overall, for the FAS and the Enrolled Analysis Set. A similar summary will be provided for the Dose Adjustment Analysis Set. Summaries of UC disease characteristics at induction baseline and maintenance baseline by ADT-failure status will be provided based on the FAS. In addition, the distribution of participants by region, country, and site ID will be presented based on the FAS and the Enrolled Analysis Set unless otherwise noted.

Continuous Variables:	Summary Type
Demographic Variables at Week I-0	
Age (years)	1
Weight (kg)	
Height (cm)	
Disease Characteristics at Week I-0	
UC disease duration (years)	
Mayo score	
Partial Mayo score	Descriptive statistics (N,
Modified Mayo score	mean, SD, median and range
CRP	[minimum and maximum],
Fecal Calprotectin	and IQ range).
Albumin	
Disease Characteristics at Week M-0	
Mayo score	
Partial Mayo score	
Modified Mayo score	
CRP	
Fecal Calprotectin	
Categorical Variables	Summary Type
Demographic Variables at Week I-0	
Sex (male, female, unknown, undifferentiated)	
Race ^a (American Indian or Alaska Native, Asian, Black or African American,	
Native Hawaiian or other Pacific Islander, White, Not Reported, Multiple)	-
Ethnicity (Hispanic or Latino, not Hispanic or Latino, Not Reported)	
Region (Eastern Europe, Asia-Pacific, Rest of World)	
Age (< $65, \ge 65$)	
Disease Characteristics at Week I-0	
Severity of UC disease (moderate: $6 \le Mayo \text{ score} \le 10$, severe: Mayo score >	Frequency distribution with
10)	the number and percentage of
Mayo endoscopy subscore at baseline (Moderate: Subscore of 2, Severe:	participants in each category.
Subscore of 3)	participants in cach category.
Modified Mayo score of 5 – 6 (moderate)	-
Modified Mayo score of 7 – 9 (severe)	
Extraintestinal manifestations (absent, present)	
Abnormal CRP (> 3 mg/L)	
Abnormal fecal calprotectin (> 250 mg/kg)	
Fecal calprotectin (> 150 mg/kg)	_
Extent of disease (limited, extensive)	

Table 6: Demographic Variables and Disease Characteristics

Tobacco or nicotine use status (non-user, prior user, current user)	
Disease Characteristics at Week M-0	
Abnormal CRP (> 3 mg/L)	
Abnormal fecal calprotectin (> 250 mg/kg)	
Fecal calprotectin (> 150 mg/kg)	
Endoscopic healing	
Endoscopic normalization	
Clinical remission status (Yes/No)	
IBDQ remission (Yes/No)	

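### The endoscopic normalization test at Week M-44 omits the endpoint's own status at re-randomization; adding it is a cheap change, but the power gain depends on an association the plan does not give

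*SAP*

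**What the plan says.** SAP 5.4.1.3 gives one test for every major secondary endpoint except maintenance of remission: "a CMH test (2-sided) stratified by clinical remission status at maintenance baseline (Yes/No) and induction dose treatment". Induction treatment has three levels, so there are 2 x 3 = 6 strata. Protocol 9.4.2.3.3 names the same two factors.

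SAP Table 3 has the row "Endoscopic normalization at Week M-44": 18% on placebo, 29% on guselkumab, power 65%. SAP Section 3 states that "sample size/power calculations were based on the chi-square test to detect a significant difference", so the 65% belongs to an unstratified test.

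Status at Week M-0 is available. Protocol Table 1 schedules an endoscopy at Weeks I-12 and I-24. Protocol Table 2, footnote h, carries those results over to Week M-0: "For all assessments not marked at this visit, data from the study assessments performed at the Week I 12 visit". SAP Appendix 3, Table 6, lists "Endoscopic normalization" among the Week M-0 disease characteristics.

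**The concern.** For a binary endpoint assessed after re-randomization, the participant's status on that endpoint at re-randomization is the natural covariate. The plan applies this elsewhere: the primary endpoint is stratified by its own Week M-0 status (SAP 5.3.2.1.1), and the MMRM and ANCOVA models include the respective baseline value (SAP 5.5.3). Endoscopic normalization instead inherits the primary endpoint's baseline, without a stated reason.

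That baseline is an imperfect proxy. A participant with subscore 1 and no symptoms can share a stratum with one at subscore 0, and a participant at subscore 0 who still has symptoms falls in the non-remission stratum. What is at stake is precision, in the confirmatory test with the least power.

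**Working it through.** **1. The plan's own figure.** Inputs from SAP Section 3 and Table 3: 161 per group, 18% vs 29%, two-sided 0.05. The pooled rate is 0.235.

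- Null SE = sqrt(2 x 0.235 x 0.765 / 161) = 0.04726
- Alternative SE = sqrt((0.18 x 0.82 + 0.29 x 0.71) / 161) = 0.04686
- z = (0.11 - 1.96 x 0.04726) / 0.04686 = 0.371, so power = 64.5%

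The stated 65% is reproduced.

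**2. The right comparator.** The planned test is a six-stratum CMH, so any gain must be measured against its power and not against 65%. I simulated CMH tests at 161 per arm with marginal rates fixed at 18% and 29%. Remission at Week M-0 was set at 33%, because Protocol Table 9 assumes that "about 33% of participants in the primary analysis population (53 participants per treatment group) will be in clinical remission at Week M-0".

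The following are assumptions, because the documents do not give them:
- normalization at Week M-0: 10% to 30%
- share of those also in remission: 60% to 95%
- odds ratio (OR) of Week M-0 remission: 1 to 3
- induction groups: 20%, 54% and 26%
- the same treatment OR in every stratum

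Over this range, with the normalization OR varied from 1 to 15, the planned test reaches about 63% to 84%.

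**3. Adding the stratum (6 to 12 strata).** Change in power against the planned CMH, 45 scenarios per row. The OR is that of Week M-0 normalization for Week M-44 normalization, given remission status.

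| Conditional OR | Min | Median | Max | Share with +5 or more |
|---|---|---|---|---|
| 1 | -1.5 | -0.9 | -0.3 | 0% |
| 2 | -0.9 | -0.5 | +0.2 | 0% |
| 4 | 0.0 | +1.3 | +2.8 | 0% |
| 6 | +0.8 | +2.9 | +4.9 | 0% |
| 8 | +0.8 | +4.3 | +7.0 | 42% |
| 10 | +2.0 | +5.6 | +8.6 | 60% |
| 15 | +2.6 | +8.4 | +12.1 | 93% |

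In the central case (20% normalized at Week M-0, 80% of them in remission, remission OR 2):
- OR 4: 67.2% to 68.9%
- OR 6: a gain of about 3 to 4 points
- OR 8: 69.4% to 74.7%
- OR 15: 70.5% to 80.4%

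Type I error of the 12-stratum test was 4.9% to 5.0%.

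**4. What OR 8 means.** In the central case it corresponds to placebo normalization at Week M-44 of about 54% in those normalized at Week M-0 and about 9% in the others. Check: 0.20 x 54% + 0.80 x 9% = 18%.

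**5. The nearest figure in the documents.** Table 3 allows the own-baseline association to be derived for clinical remission, a different endpoint.

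- Placebo: 25% overall and 36% in the 33% in remission at Week M-0. The others: (0.25 - 0.33 x 0.36) / 0.67 = 19.6%. OR = (0.36/0.64) / (0.196/0.804) = 2.3.
- Guselkumab: 45% and 61%. The others: (0.45 - 0.33 x 0.61) / 0.67 = 37.1%. OR = (0.61/0.39) / (0.371/0.629) = 2.6.

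If normalization behaved the same way, the gain would be close to zero.

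**6. Sparse cells.** With 20% normalized and a fifth of those outside remission, 161 x 0.20 x 0.20 = about 6 participants per arm are spread over three induction groups.

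**The case against.** The planned choice is defensible. Both CMH factors are randomization factors (SAP 1.3), they are applied uniformly, and the sponsor aimed for at least 90% power only for most of the major secondary endpoints. The lower power here is disclosed. The same argument could be made for endoscopic healing or IBDQ remission. All of this stands: the plan contains no error here, and the test is valid as written.

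The benefit is also diluted. The endpoint is ninth of nine in the global order (SAP 5.4.1), so it counts only if the eight before it pass. Maintenance of remission, just ahead of it, has 74% stated power. On the Table 3 powers, including the primary endpoint, the chance of reaching this test is at most 74%, and about 55% if the tests were independent. A 5-point gain would then be worth about 0.55 x 5 = 2.8 to 0.74 x 5 = 3.7 points of confirmatory success. The US order is in a figure that is not shown.

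A reader might infer that the change buys 5 points or more at no cost. The documents do not support the size: 5 points never occurred at a conditional OR of 6 or less. Nor is it free, given the sparse strata and the possible small loss.

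A reader might also scale the unstratified variance by 1 - rho^2 and, at rho = 0.5, report a rise from 64.5% to 76.9%. That credits the new stratum with precision that the planned CMH already has. With 20% normalized at Week M-0 and 23.5% overall at Week M-44, rho = 0.5 would also need about 66% vs 13%, an OR near 13.

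**Conclusion.** The point holds as a minor improvement. The test of endoscopic normalization leaves out a relevant baseline variable that is already collected. Using it would follow the plan's own practice for the primary and continuous endpoints.

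The size is not established. It rests on the Week M-0 prevalence of normalization and on how strongly it persists to Week M-44 beyond what remission status already explains, and neither figure is in the documents. The possible upside is larger than the possible loss, but how likely that upside is cannot be judged from the documents. Their only analogue points to the low end.

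**What to change.** Before the Week M-44 database lock and unblinding, add to SAP 5.4.1.3, for endoscopic normalization only, Week M-0 endoscopic normalization (Yes/No, final reported subscore, missing counted as not normalized) as a further CMH stratum. Use it for both the test and the CMH-weighted difference, and keep remission and induction treatment.

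Because Protocol 9.4.2.3.3 names the existing strata, record this in SAP Appendix 2, which now states that the protocol-planned analyses are unchanged.

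Pooled blinded data can first show the prevalence, the association and the cell counts. If 12 strata prove too sparse, replacing remission by normalization (6 strata) gave nearly the same power in the central case (69.1%, 75.0% and 81.0% at OR 4, 8 and 15), but it drops a randomization factor from the test.

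The cost is a short SAP amendment. No participants, visits or data are added.

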5.4.1.4. Subgroup Analyses

The consistency of treatment effect for the major secondary endpoints will be evaluated for the subgroups defined in Section 5.10.6. for the major secondary endpoints. Note that, for subgroup analyses, the analysis sets are the individual subgroups of the **Randomized Full Analysis Set**. For each of these subgroups, the rate (risk) difference of each guselkumab group vs placebo and the associated 95% confidence interval will be provided. The rate (risk) difference and confidence intervals will be provided based on the Cochran-Mantel-Haenszel weight that includes factors for clinical remission status at maintenance baseline (Yes/No), and induction dose treatment (guselkumab 400 mg, guselkumab 200 mg, placebo crossover to guselkumab 200 mg). For the subgroup analyses based on the maintenance stratification factors, the corresponding factor will not be included in the model. The main estimand for the major secondary endpoints will be used for these subgroup analyses and the missing data rule (i.e., missing values will be imputed as nonresponder) used for the secondary estimands will be applied.

